8.1.2 Clinical Laboratory Tests

All available clinical laboratory tests results will be listed.

8.1.3 Vital Signs

Vital signs are taken at Screening, baseline, Month 3, and Month 6/End of Treatment of. Assessments will include orthostatic (supine and standing) blood pressure and heart rate. In addition, body weight and waist circumference are measured at baseline, Week 24/End of Treatment of, and every 48 weeks. BMI is calculated for each visit at which body weight is measured. The potential clinically relevant vital sign abnormalities are listed by subject. Criteria for the potential clinically relevant vital sign abnormalities are provided in [Appendix 1](#). Incidences of clinically relevant vital signs abnormalities based on the observation from the scheduled and unscheduled post-baseline visits.

If vital sign assessments are repeated for the same visit, the last repeat values are used for production of summary tables. This is accomplished by sorting patient data by visit date and visit time (if applicable) within the same visit identification.

Protocol 31-201-301 Interim Analysis Plan

8.1.4 Electrocardiogram Results

Twelve (12)-lead ECGs are recorded at Screening only; results will be provided in a listing.

8.1.5 Physical Examination

Physical examination data are listed by subject.

8.1.6 Columbia Suicide Severity Rating Scales

Columbia Suicide Severity Rating Scales (C-SSRS) are assessed at baselines, and at Month 3 and Month 6. C-SSRS data at baseline are summarized for incidence of reporting:

- Suicidality
- Suicidal behavior (and its 4 types)
- Suicidal Ideation (and its 5 types)

Suicidality is defined as reporting at least one occurrence of any suicidal behavior or suicidal ideation. Suicidal behavior is defined as reporting any type of suicidal behaviors (actual attempt, interrupted attempt, aborted attempt and preparatory acts or behavior). Suicidal ideation is defined as reporting any type of suicidal ideation. In addition to the above three incidences, C-SSRS data collected from post-baseline are also summarized for incidence of reporting:

- Complete suicidality
- Emergence of suicidal ideation
- Emergence of serious suicidal ideation
- Worsening of suicidal ideation
- Emergence suicidal of behavior

Any completed suicide is considered as complete suicidality. Emergence of suicidal ideation is defined as having no suicidal ideation at baseline and reporting any type of ideation during treatment. Emergence of serious suicidal ideation is defined as having no suicidal ideation at baseline and reporting any type of suicidal ideation with ideation severity rating of 4 or 5 during treatment. Worsening of suicidal ideation is defined to occur when the most severe suicidal ideation rating during treatment is more severe than its rating at baseline. Emergence of suicidal behavior is defined as having no suicidal behavior at baseline and reporting any type of suicidal behavior during treatment.

Protocol 31-201-301 Interim Analysis Plan

The suicidal ideation intensity total score is the sum of intensity scores of 5 items (frequency, duration, controllability, deterrents and reasons for ideation). The score of each intensity item ranges from 0 (none) to 5 (worst) which leads to the range of the total score from 0 to 25. A missing score of any item for will result in a missing total score. If no suicidal ideation is reported, a score of 0 is given to the intensity scale.

The incidence of C-SSRS events and change from baseline in suicidal ideation intensity total scores are presented by nominal study visits as recorded in CRF without mapping to time window of the study week/month.

8.2 Other Data Analysis

8.2.1 Exposure to Study Medication

Exposure to study medication will be summarized for all subjects entered and for completers of Month 1-3, respectively. Descriptive statistics will be presented for days of exposure. Number (percent) of subjects staying on MyCite at Month 4-6 will also be provided.

8.2.2 Compliance to Study Medication

The number of subjects who missed study doses (excluding missed study doses due to premature discontinuation from the study) will be summarized by number of study dose missed. This summary will be performed with the ITT analysis set. A corresponding listing of subjects with missed doses during the study periods will be provided.

8.2.3 Concomitant Medication

Non-CNS concomitant medications (taken 30 days prior to the study entry through end of study) and CNS-active concomitant medications (taken 7 months prior to the study entry through end of study) will be summarized. Number and proportion of patients taking concomitant medications will be tabulated for Safety Sample of each drug classification using the B2 Enhanced version of WHODrug B3G (March 2020), for prior to, during and the post the study medication treatment period (including oral aripiprazole tablets).

8.2.4 Protocol Deviation

Protocol deviations will be listed and tabulated by protocol deviation type and centers.

In addition, protocol deviations affected by the COVID-19 will be summarized. Listing of subjects with protocol deviations affected by the COVID-19 will also be provided.

Protocol 31-201-301 Interim Analysis Plan

9 Interim Analysis

Two interim analysis are planned when 50% and 70% of subjects have completed the prospective phase (Months 1-3). At the end of the interim analysis, a decision will be made to continue with/without sample size increase, stop for efficacy or stop for fertility based on the p-value and conditional power from the interim data (as described in [Table 9-1](#)). Subjects will continue to be enrolled into the trial during the interim analysis; if the trial is stopped due to futility, all randomized subjects will be terminated; however, if the interim analysis stops the trial for efficacy, then all randomized subjects will continue until the last observation. Subjects in screening will be discontinued and no further randomization will occur. The 2-sided alpha levels for these 2 interim analyses are 0.00312 and 0.0139 respectively, and the alpha left for the final analysis will be 0.04528. The sample size will be re-estimated only based on the conditional power determined at the interim analysis. The adaptive designs methodology published by Chen, Dements and Lan (2004) will be used to increase the sample size based on the estimate of the treatment effect size of the primary efficacy endpoint at interim, possibly combined with other external information, without inflating the Type I error. Should the timing or frequency of the interim analysis be different from the previously specified, stopping boundary would be re-calculated using the alpha spending function.

Based on the interim analysis results, the trial sample size will be adjusted according to [Table 9-1](#). While the interim analysis follows the boundaries listed in [Table 9-1](#), “final” analysis must be performed after a recommendation based on the interim analysis. This “final” analysis will include any subjects that met the criteria of analysis between the data cutoff for the interim analysis and the final database lock, and the alpha level for the “final” analysis will be derived based on the total number of subjects enrolled using O’Brien-Fleming spending function.

Table 9-1 Sample Size Re-estimation Schemes		
Interim Results	Interim Analysis Recommendation	Sample Size (completers)
P – value less than specified alpha level at interim	Stop for efficacy	About 112 or 157
Conditional power $\geq 80\%$	No adaption to the planned sample size	224
Conditional power $\geq 50\%$ and $< 80\%$	Increase sample size up to 300	300

Protocol 31-201-301 Interim Analysis Plan

Table 9-1 Sample Size Re-estimation Schemes		
Interim Results	Interim Analysis Recommendation	Sample Size (completers)
Conditional power $\geq 15\%$ and $< 50\%$	No adaption to the planned sample size	224
Conditional power $< 15\%$	Stop the trial for futility	About 112 or 157

10 References

3. YHJ Chen, DL DeMets and KKG Lan Increasing the sample size when the unblinded interim result is promising. *Statist. Med.*2004, 23 1023—1038

Protocol 31-201-301 Statistical Analysis Plan

Appendix 1 Criteria for Potential Clinical Relevance Vital Signs Abnormalities

Variable	Criterion Value ^a	Change Relative to Baseline ^a
Heart Rate ^b	> 120 bpm < 50 bpm	≥ 15 bpm increase ≥ 15 bpm decrease
Systolic Blood Pressure ^b	> 180 mmHg < 90 mmHg	≥ 20 mmHg increase ≥ 20 mmHg decrease
Diastolic Blood Pressure ^b	> 105 mmHg < 50 mmHg	≥ 15 mmHg increase ≥ 15 mmHg decrease
Orthostatic Hypotension	≥ 20 mmHg decrease in systolic blood pressure and a ≥ 25 bpm increase in heart rate from supine to sitting/standing	Not Applicable (baseline status not considered)
Weight	-	≥ 7% increase ≥ 7% decrease

^a In order to be identified as potentially clinically relevant, an on-treatment value must meet the “Criterion Value” and also represent a change from the subject’s baseline value of at least the magnitude shown in the “Change Relative to Baseline” column.

^b As defined in “Supplementary Suggestions for Preparing an Integrated Summary of Safety Information in an Original NDA Submission and for Organizing Information in Periodic Safety Updates,” FDA Division of Neuropharmacological Drug Products draft (2/27/87).

Appendix 2 Table of Contents for Proposed Tables and Listings**Summary Tables:**

- CT-1.1 Subject Disposition by Site (Enrolled Sample)
- CT-2.1 Reasons for Discontinuation (ITT Sample)
- CT-2.2 Discontinuation from treatment / study due to COVID
- CT-3.1.1 Demographic Characteristics by Gender and Site and Overall (ITT Sample)
- CT-3.1.2 Demographic Characteristics by Gender and Site and Overall (Month 1-3 mITT)
- CT-3.2.1.1 Baseline Disease Characteristics by Gender and Site and Overall (ITT Sample)
- CT-3.2.2.1 Baseline Disease Characteristics by Gender and Site and Overall (Month 1-3 mITT)
- CT-4.1.1 Medications Taken Prior to Start of Trial (Safety Sample)
- CT-4.2 Medications Taken During Trial (Safety Sample)
- CT-4.3 Medications Taken Post Trial (Safety Sample)
- CT-4.4.1 Listing of ConMeds due to COVID
- CT-4.4.2 Summary of Protocol Deviations (ITT Sample)

Protocol 31-201-301 Statistical Analysis Plan

CT-5.1.1 Analysis of Inpatient Psychiatric Hospitalization Rate Between the Retrospective Period Month 1-3 and the Prospective Period Month 1 - 3 (Month 1-3 mITT)

CT-5.1.2 Analysis of Inpatient Psychiatric Hospitalization Rate Between the Retrospective Period Month 1-3 and the Prospective Period Month 1 - 3 (ITT Sample)

CT-5.1.3 Analysis of Inpatient Psychiatric Hospitalization Rate Between the Retrospective Period Month 1-3 and the Prospective Period Month 1 - 3 (Month 1-3 mITT and Completer)

CT-5.1.2.1 Number of Inpatient Psychiatric Hospital Stays Per Subject Between Retrospective Period and Prospective Period Month 1-3 (Month 1-3 mITT)

CT-5.1.2.2 Number of Inpatient Psychiatric Hospital Stays Per Subject Between Retrospective Period and Prospective Period Month 1-3 (ITT Sample)

CT-5.1.2.3 Cumulative Duration of Inpatient Psychiatric Hospitalization Per Subject Between Retrospective Period and Prospective Period Month 1-3 (Month 1-3 mITT)

CT-5.2.3.4 Cumulative Duration of Inpatient Psychiatric Hospitalization Per Subject Between Retrospective Period and Prospective Period Month 1-3 (ITT Sample)

CT-5.1.2.5 Mean Duration of Inpatient Psychiatric Hospitalization Per Subject Between Retrospective Period and Prospective Period Month 1-3 (Month 1-3 mITT)

CT-5.1.2.6 Mean Duration of Inpatient Psychiatric Hospitalization Per Subject Between Retrospective Period and Prospective Period Month 1-3 (ITT Sample)

CT-5.2.1 Summary of PDC for Month 1-3 Retrospective/Prospective Period (ITT Sample)

CT-5.2.2 Comparison of PDC Adherence for Month 1-3 Retrospective/Prospective Period (ITT Sample)

Protocol 31-201-301 Statistical Analysis Plan

- CT-6.2.1 Summary of number of dashboard access by month and overall (ITT)
- CT-6.2.2 Summary of features the physician/caregiver focus on discussion/decision making by month and overall (ITT)
- CT-6.2.3 Summary of medical/treatment decisions made as a result of MyCite data by month and overall (ITT)

- CT-6.6.1 Summary of features the physician/caregiver focus on in discussion/decision making
- CT-6.6.2 Summary of medical/treatment decisions made as a result of MyCite data
- CT-6.6.3 Summary of number of dashboard access
- CT-6.4 Number (%) visits done remotely due to COVID

- CT-7.1 Extent of Exposure to Study Medication - (Safety Sample)
- CT-7.2 Summary statistics of Exposure to Study Medication (Safety Sample)

- CT-8.1 Adverse Events (All Causalities) By Treatment-Safety Sample
- CT-8.2.1 Incidence of Treatment-emergent Adverse Events by System Organ Class and MedDRA Preferred Term (Safety Sample)
- CT-8.2.2 Incidence of Treatment-emergent Adverse Events by System Organ Class, MedDRA Preferred Term and Severity (Safety Sample)
- CT-8.3.1 Incidence of Treatment-emergent Adverse Events by System Organ Class and MedDRA Preferred Term (Safety Sample)
- CT-8.3.2 Incidence of Treatment-emergent Adverse Events by System Organ Class, MedDRA Preferred Term and Severity (Safety Sample)
- CT-8.4.1 Incidence of Serious Treatment-emergent Adverse Events by System Organ Class and MedDRA Preferred Term (Safety Sample)
- CT-8.4.2 Incidence of Serious Treatment-emergent Adverse Events by System Organ Class, MedDRA Preferred Term and Severity (Safety Sample)
- CT-8.5.1 Incidence of Discontinuation of Treatment Due to Treatment-Emergent Adverse Events by System Organ Class and MedDRA Preferred Term (Safety Sample)
- CT-8.5.2 Incidence of Discontinuation of Treatment Due to Treatment-Emergent Adverse Events by System Organ Class, MedDRA Preferred Term and Severity (Safety Sample)
- CT-8.6.1 Incidence of Non-serious Treatment-Emergent Adverse Events Greater Than or Equal to 5% in Any Group by System Organ Class and MedDRA Preferred Term (Safety Sample)

Protocol 31-201-301 Statistical Analysis Plan

CT-8.6.2 Occurrence (Number of Events) of Non-serious Treatment-emergent Adverse Events with Incidence Greater Than or Equal to 5% in Any Group by System Organ Class and MedDRA Preferred Term (Safety Sample)

CT-8.7.1 Incidence of Serious Treatment-emergent Adverse Events by System Organ Class and MedDRA Preferred Term (Safety Sample)

CT-8.7.2 Occurrence (Number of Events) of Serious Treatment-emergent Adverse Events by System Organ Class and MedDRA Preferred Term (Safety Sample)

CT-8.8 Occurrence (Number of Events) of Potentially Medication or Serious Treatment-emergent Adverse Events by System Organ Class and MedDRA Preferred Term (Safety Sample)

CT-8.9 Incidence of Device-related Treatment-Emergent Adverse Events by System Organ Class, MedDRA Preferred Term and Severity (Safety Sample)

CT-8.9 Incidence of Device-related Treatment-Emergent Serious Adverse Events by System Organ Class, MedDRA Preferred Term and Severity (Safety Sample)

CT-8.11 Frequency of Subjects with Skin Irritation Scores Related to Patch (Safety Sample)

CT-8.12 Incidence of Patch-related Treatment-Emergent Adverse Events with Skin Irritation Score ≥ 2 by System Organ Class, MedDRA Preferred Term and Severity (Safety Sample)

CT-8.13 Columbia-Suicide Severity Rating Scale(C-SSRS), Suicidality (Safety Sample)

CT-8.14 Columbia-Suicide Severity Rating Scale(C-SSRS) Suicidality Change during Post-baseline (Safety Sample)

CT-8.15 Summary of the suicidal ideation intensity total score (Safety Sample)

CT-11.1 Criteria for Potentially Clinically Relevant Abnormalities in Vital Signs

CT-11.2.1 Listing of Potentially Clinically Relevant Abnormalities in Vital Signs During the Prospect Treatment Period (Safety Sample)

CT-11.2.2 Incidence of Potentially Clinically Relevant Abnormalities in Vital Signs During the Prospect Treatment Period (Safety Sample)

CT-11.2.3 Mean Change from Baseline of the Double-Blind Treatment Period in Vital Signs During the Prospect Treatment Period (Safety Sample)

Listings:

CT-9.1 Listing of Deaths (Safety Sample)

CT-9.2 Listing of Serious Adverse Events (Safety Sample)

CT-9.3 Listing of Discontinuation of Treatment Due to Adverse Events (Safety Sample)

CT-9.4 Listing of Patch-related Treatment-emergent Adverse Events (Safety Sample)

CT-9.5 AE listing for subjects with confirmed or presumed diagnosis of COVID

AE-1.1 Adverse Events for All Enrolled Subjects

DREAS-1 Discontinued Subjects and Reason for Discontinuation

DREAS-2 Adverse Events for Subjects Who Withdrew Consent

EFF-1.1 Prior and Post Inpatient Psychiatric Hospitalization for mITT – Month 1-3

EFF-1.2 Prior and Post Inpatient Psychiatric Hospitalization for mITT – Month 4-6

EFF-1.3 Prior and Post Inpatient Psychiatric Hospitalization for ITT Sample

EFF-1.4 Prior and Post All Other (non-inpatient) Psychiatric Treatment Visits Excluding Inpatient Psychiatric Hospitalization for ITT Sample

EFF-1.5 PDC by Subject (ITT Sample)

[REDACTED]

Protocol 31-201-301 Statistical Analysis Plan

PDATA-1.1.1 Consent and Eligibility
 PDATA-1.1.2 Inclusion Criteria and Exclusion Criteria
 PDATA-2 Subject Enrollment List
 PDATA-3.1 Subject Disposition
 PDATA-3.2 Study Completion Status and Reasons for Discontinuation
 PDATA-4 Demographics Characteristics
 PDATA-5.1 Psychiatric History
 PDATA-5.2 Diagnosis of Schizophrenia
 PDATA-6.1 Concomitant Medications: Medications Taken Prior to Start of Study
 PDATA-6.2 Concomitant Medications: Medications Taken During Study
 PDATA-6.3 Concomitant Medications: Medications Taken Post Study
 PDATA-7.1 Study Medication - MyCite
 PDATA-7.5 Study Medication Accountability – Abilify MyCite
 PDATA-8 Medical History
 PDATA-9 Physical Examination
 PDATA-10 Adverse Events
 PDATA-11 Vital Signs
 PDATA-12.1 Electrocardiogram Results
 PDATA-12.2 Electrocardiogram Results - Raw 3 Beat Data
 PDATA-13.1 Hospitalization and Medical Interventions - 6 Months Retrospective Period
 PDATA-13.2 Hospitalization and Medical Interventions - Prospective Period

PDATA-17.1 Visual Analog Scale for Subject-reported Rating of Injection Site Pain
 PDATA-17.2 Investigator Assessment of Most Recent Injection Site

PDATA-18 Birth Control Status
 PDATA-19 Screening Failures
 PDATA-20 Follow-up
 PDATA-21 Protocol Deviations - CRF
 LAB-1 Laboratory Test Results: Urine Pregnancy Test
 PDEV-1 Protocol Deviations by Center and Type of Deviation
 PDEV-2 Protocol Deviations by Subject
 PDEV-3 Protocol Deviations Criteria

Figures:

Figure 5.1 Kaplan-Meier Curve of Time to Discontinuation Due to All Causes

This page is a manifestation of an electronically captured signature

SIGNATURE PAGE

Document Name: P031_201_00301_Statistical Analysis Plan Final

Document Number: 1000105170

Document Version: 2.0

Signed by	Meaning of Signature	Server Date (dd-MMM- yyyy hh:min) - UTC timezone
[REDACTED]	Biostatistics Approval	05-Nov-2020 21:15:23
[REDACTED]	Clinical Approval	05-Nov-2020 13:56:51

Otsuka Pharmaceutical
Development & Commercialization, Inc.

Investigational Medicinal Product

Aripiprazole (OPC-14597)

Protocol No. 031-201-00301

A Phase IIIb Multi-Center, Open-Label, Mirror-Image, Trial in Adult Subjects with

2.1 Sample Size and Power Justification

The primary endpoint of this trial compares the paired proportions of inpatient psychiatric hospitalization during the retrospective period (Month 1 to 3) and the prospective period (Month 1 to 3), which will be analyzed using a McNemar test.

Based on published results of other similar studies for the particular time periods (retrospective Month 1 to 3 and prospective Month 1 to 3) we are evaluating, it is reasonable to assume that 15.5% of the subjects are hospitalized during retrospective Month 1 to 3 and 7% are hospitalized during prospective Month 1 to 3; about 5% of subjects who are not hospitalized retrospectively will be hospitalized prospectively, while 13.5% of the subjects who are hospitalized retrospectively will not be hospitalized. With this assumption, 200 completed subjects will provide 80% power ($\alpha = 0.05$ two-sided) to detect a difference of 8.5% in the paired hospitalization proportions between pre-switch and post-switch periods while the proportion of total discordant pairs is 18.5%. In addition, this sample size will provide 80% power for the comparison of retrospective Month 4 to 6 vs prospective Month 4 to 6, assuming 30% of the subjects are hospitalized pre-switch (12.5% subjects will be hospitalized post-switch and another 17.5% won't have hospitalization post-switch) and, overall, 20% are hospitalized post-switch (among them, 12.5% subjects are hospitalized both pre-switch and post-switch and 7.5% have no hospitalization pre-switch).

Two interim analyses are planned at when 50% and 70% of subjects have completed the prospective period (Month 1 to 3); in order to conserve the overall Type I error at 0.05 level, 224 evaluable subjects are needed to complete the 3-month treatment to maintain 80% power. This sample size assumes the 3 sequential tests are made using LanDeMets Spending Function with O'Brien-Fleming boundary, a futility conditional power of 15% is built in the sample size calculation to allow the trial to stop for futility. Based on the conditional power and the alpha level at the interim analysis, the trial could stop for efficacy or futility, continue with the initially planned 224 sample size or increase to up to 300 if the conditional power fall between 30% to 80% ([Section 2.2](#)). The 2-sided alpha

Protocol 31-201-301 Interim Analysis Plan

levels for these 2 interim analyses are 0.00312 and 0.0139 respectively, and the alpha left for the final analysis will be 0.04528.

2.2 Interim Efficacy Analysis

The purpose of the interim analyses is to decide whether there is sufficient evidence that the study will be stopped to declare efficacy or futility, or addition subjects are needed to have sufficient power to achieve the primary objective.

The primary endpoint of this trial is the comparison of inpatient psychiatric hospitalization rates (proportion of subjects with ≥ 1 inpatient psychiatric hospitalization[s]) between the retrospective period (Months 1 to 3) while on oral standard-of-care antipsychotic treatment and the prospective period (Months 1 to 3) after the switch to Abilify MyCite.

The analysis on the primary endpoint will be performed using a McNemar test, those who have hospitalization data during Months 1 to 3 prior to the screening period and during Months 1 to 3 after switch to Abilify MyCite for the modified Intent-to-Treat (mITT) sample; this will be a 2-sided test.

Two interim analysis are planned when 50% and 70% of subjects have completed the prospective phase (3 months). At the end of the interim analysis, a decision will be made to continue with/without sample size increase, stop for efficacy or stop for futility based on the p-value and conditional power from the interim data (as described in [Table 2-1](#)). Subjects will continue to be enrolled into the trial during the interim analysis; if the trial is stopped due to futility, all randomized subjects will be terminated; however, if the interim analysis stops the trial for efficacy, then all randomized subjects will continue until the last observation. Subjects in screening will be discontinued and no further randomization will occur. The 2-sided alpha levels for these 2 interim analyses are 0.00312 and 0.0139 respectively, and the alpha left for the final analysis will be 0.04528. The sample size will be re-estimated only based on the conditional power determined at the interim analysis. The adaptive designs methodology published by Chen, Dements and Lan (2004) will be used to increase the sample size based on the estimate of the treatment effect size of the primary efficacy endpoint at interim, possibly combined with other external information, without inflating the Type I error. Should the timing or frequency of the interim analysis be different from the previously specified, stopping boundary would be re-calculated using the alpha spending function.

Based on the interim analysis results, the trial sample size will be adjusted according to [Table 2-1](#).

Protocol 31-201-301 Interim Analysis Plan

Interim Results	Interim Analysis Recommendation	Sample Size (completers)
P – value less than specified alpha level at interim	Stop for efficacy	About 112 or 157
Conditional power \geq 80%	No adaption to the planned sample size	224
Conditional power \geq 30% and $<$ 80%	Increase sample size up to 300	300
Conditional power \geq 15% and $<$ 30%	No adaption to the planned sample size	224
Conditional power $<$ 15%	Stop the trial for futility	About 112 or 157

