2.2.2 Sensitivity Analysis

As sensitivity analysis, the primary efficacy analysis will be performed on the mITT subjects who have completed the 3-month treatment only.

3 Data Analysis

The interim analysis will be performed by the Otsuka Pharmaceuticals. The interim analysis plan will be finalized before the first interim analysis.

Protocol 31-201-301 Interim Analysis Plan

In addition to the efficacy analysis mentioned in [Section 2](#), subject disposition, reasons for discontinuation, demographics and baseline disease characteristics will be summarized. Summary statistics will consist of mean, median, range, and standard deviation (SD) for continuous variables and tabulations of frequency distributions for categorical variables.

The dashboard data will be summarized by month and Month 3. The summary statistics of dashboard access by month and Month 3 will be provided. The count and percentage of features on decision/discussion making and general medical/treatment decisions made as a result of MyCite data will be summarized per the categories collected on the CRF.

The incidences of the treatment-emergent adverse events (TEAEs) serious adverse event (SAE) are summarized by system organ class, preferred term and by severity and relationship to study treatment. Discontinuation due to TEAEs will also be summarized. For the first interim analysis at about 50% of the subjects complete 3 months treatments, only data up to Month 3 (including AEs and SAEs) will be included in the analysis..

4 Confidentiality of Results

Interim database will be cleaned and frozen for the interim analysis. The decision to continue or stop the trial will be strictly based on the prespecified criteria in [Table 2-1](#).

An internal IARC will be set up from clinical and statistics functions to make the decision based on the interim analysis results and the prespecified criteria.

5 References

YHJ Chen, DL DeMets and KKG Lan Increasing the sample size when the unblinded interim result is promising. *Statist. Med.* 2004, 23 1023—1038.

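### Undefined external information may feed the sample-size increase, against the conditional-power-only rule, so the claim of no Type I error inflation is unsupported as written

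*SAP*

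**What the plan says.** The same text stands in Protocol 7.4.4, SAP section 9 and section 2.2 of the Interim Analysis Plan supplied with the SAP.

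- The interim decision (continue with or without an increase, stop for efficacy, stop for futility) rests on the p-value and conditional power from the interim data, as laid out in the decision table.
- "The sample size will be re-estimated only based on the conditional power determined at the interim analysis".
- The next sentence says a published adaptive method will be used to increase the sample size from the interim estimate of the effect, "possibly combined with other external information, without inflating the Type I error".

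The decision tables (Protocol Table 7.4.4-1, SAP Table 9-1, Interim Analysis Plan Table 2-1) have rows for the p-value and for conditional power and nothing else. Interim Analysis Plan section 4 adds: "The decision to continue or stop the trial will be strictly based on the prespecified criteria". That sentence covers continuing or stopping. The size of the trial is tied to the table separately, in 2.2.

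The increase row is 30% to 80% conditional power in the protocol and the Interim Analysis Plan, and 50% to 80% in the SAP body. It allows an increase up to 300.

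**The concern.** The two adjacent sentences cannot both govern. If only conditional power from the interim data counts, external information has no role. If external information may enter, the rule is no longer conditional power alone, and nothing says which information, with what weight, or whether it is fixed before the interim results are seen.

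What is at stake is the stated Type I error property. A conventional final test after an increase keeps its error rate when the increase is made on a sufficiently promising interim trend in the trial itself. An outside effect estimate can raise the calculated conditional power when the trial's own trend is weaker, which is where adding subjects raises the chance of a false rejection. The trial is open-label, the sponsor performs the interim analysis and an internal committee decides, so a reader could not later verify which rule had been applied.

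**Working it through.** **Inputs.** Interim Analysis Plan 2.1 and 2.2 give a 2-sided test, a planned size of 224, and looks at 50% and 70% (about 112 and 157). The alphas are "0.00312 and 0.0139 respectively, and the alpha left for the final analysis will be 0.04528". The planned difference is 8.5 points with 18.5% discordant pairs, the increase row is 30% to 80% with a cap of 300, and futility is below 15%.

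**The plan's own figures.** "the 3 sequential tests are made using LanDeMets Spending Function with O'Brien-Fleming boundary": Lan-DeMets O'Brien-Fleming bounds at 112, 157 and 224 give 0.00305, 0.01388 and 0.04529, against the stated 0.00312, 0.0139 and 0.04528. The stated levels together give an overall error of 0.0500. Without an increase, the claim holds.

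**Formulas** (normal approximation to McNemar; z is the interim statistic at n pairs, S = z√n, c = 2.002 for alpha 0.04528).

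- Conditional power on the interim trend, planned N = 224: Φ[(S·N/n − c√N)/√(N − n)].
- Conditional power with the planning effect: Φ[(S + θ(N − n) − c√N)/√(N − n)], with θ = 0.085/√0.185 = 0.198.
- Conditional error under the null at final size N: 1 − Φ[(c√N − S)/√(N − n)].

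**Where an increase helps or hurts.** Comparing conditional error at 224 and 300, the increase lowers it when interim-trend conditional power is at least about 0.43 (first look) or 0.41 (second look), and raises it below that. At the second look:

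| Interim-trend conditional power | Conditional error at 224 | Conditional error at 300 |
|---|---|---|
| 0.15 | 0.034 | 0.050 |
| 0.30 | 0.072 | 0.081 |
| 0.50 | 0.137 | 0.126 |

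**Overall error under the null** (simulation, 30% to 80% row to 300, final alpha kept at 0.04528). Figures are twice the one-sided error in the direction favouring MyCite, so 0.050 is nominal.

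| Effect driving the increase | Futility | Error |
|---|---|---|
| Interim trend | not enforced | 0.048 |
| Interim trend | enforced on interim data | 0.039 |
| Planning effect | not enforced | 0.054 |
| Planning effect | enforced on interim data | 0.040 |
| Planning effect | also judged with the planning effect | 0.052 |

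Counting actual rejections in both directions, the two not-enforced rows become about 0.049 and 0.052 to 0.053.

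**Free choice of N by outside information, futility not enforced, cap 300.** Within the 30% to 80% row the worst case is 0.0502 to 0.0517, depending on whether the row must be met at the second look or at either look. Within 50% to 80% it is 0.0500. At any conditional power, ignoring the table, it is 0.058. With futility enforced on interim data, every one of these is 0.0425 or lower.

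**The case against.** The strongest reply is that the clause is confined by its surroundings. The decision sentence already ties the choice to conditional power from the interim data, and the external-information phrase belongs to the step of increasing the sample size, not to futility. If outside information only picks a number up to 300 inside the increase row, the effect on error is negligible. This stands, and it limits the size of the problem. It does not remove it, because no passage says the phrase is limited in that way.

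A reader might infer that the clause lets the sponsor rescue a trial due to stop for futility. At z = 0.8 with 112 pairs, conditional power is 11% on the interim trend (futility row) but 52% with the planning effect (increase row). The documents do not support that reading: the table puts this trial in the futility row, and Interim Analysis Plan section 4 makes the table binding for continuing or stopping. Such a move would breach the plan.

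SAP section 9 also says the alpha of the analysis that follows an interim recommendation will be re-derived from the total enrolled with the O'Brien-Fleming spending function. The results above keep 0.04528. Keeping the two interim levels and re-deriving at 300 gives about 0.042, and the planning-effect case without futility stops falls to about 0.051. That sentence reduces the concern without fully curing a size chosen from the data, and it appears neither in Protocol 7.4.4 nor in Interim Analysis Plan 2.2.

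**Conclusion.** The contradiction is real and appears in all three places. The assurance about Type I error is unsupported, because it is attached to an input that is not defined.

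It would go too far to conclude that error control is undone. Control depends on the conditional-power region in which the size may rise, the cap, and whether futility is enforced. With the planning effect as the external input, error moves from about 0.048 to 0.049 up to about 0.052 to 0.054 when futility is not enforced. It stays near 0.04 when futility is enforced on interim data. The 0.058 figure is a worst case that requires setting the table aside.

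These results assume looks at 112 and 157, conditional power calculated to 224, the second-look boundary kept after a first-look increase, and a normal approximation. Taking the planning effect as the external information is an assumption, since the documents name none. Outside the section 4 sentence they do not say whether futility is binding, so both cases are shown. This is worth correcting before an interim analysis, but it is modest in size.

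**What to change.** In Protocol 7.4.4, SAP section 9 and Interim Analysis Plan 2.2, delete the words before the comma in "possibly combined with other external information, without inflating the Type I error". Add one sentence: the conditional power used for both the increase row and the futility row is calculated from the effect estimated in this trial's interim data alone.

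With that change and the 30% to 80% row, Type I error is 0.0485 without futility stops and 0.0391 with them. With the SAP body's 50% to 80% row it is 0.0479 and 0.0391. All are below 0.05, so the assurance can then stand under the assumptions above.

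The cost is one phrase removed and one sentence added in three places. No analysis, sample size or alpha level changes. The sponsor gives up only a discretion that the neighbouring sentence already excludes.
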